7.4.2 Premature termination or suspension of the study or a study site

The study or the study site can be prematurely terminated or suspended by the sponsor. If and when certain issues arise affecting the conduct of this Post Approval Study, the possibility of early study termination will be discussed with the FDA prior to termination. Reasons for termination of the study or a study site may include, but are not limited to, the following:

• Subject enrollment is unsatisfactory.

⁴ Defined as a method that results in a low failure rate (i.e., less than 1% per year) when used consistently and correctly, such as implants, injectables, combined oral contraceptives, some IUDs, sexual abstinence, or vasectomized partner.

- The risks and benefits of continuing the study have been reassessed, and the risks outweigh any potential benefits.
- The incidence of AEs constitutes a potential health hazard to the subjects.
- New scientific data do not justify a continuation of the study.
- The investigator or study site exhibit serious and/or persistent non-adherence to the clinical study protocol and/or applicable regulatory requirements.
- The Sponsor decides to terminate the study at any time for any other reason.

Furthermore, the study may be prematurely ended if the regulatory authority or the IRB makes a recommendation to terminate or suspend approval for the study, the study site, or the investigator.

If the study is prematurely terminated or suspended for any reason, the investigator must inform the subjects and assure appropriate follow-up treatment. Within the timeframes noted in applicable regulations, the Sponsor will promptly inform the investigators, study sites, the IRB, and regulatory authorities of the termination or suspension of the study, as appropriate.

8 TREATMENTS

8.1 Investigational product(s)

8.1.1 Description of investigational product(s)

Radiesse injectable implant is an opaque, sterile, non-pyrogenic, semi-solid, cohesive implant. The principle component is synthetic calcium hydroxylapatite suspended in a gel carrier that consists primarily of water (sterile water for injection USP), glycerin (USP), sodium carboxymethylcellulose (USP). Radiesse injectable implant (1.5cc syringe unit) has a CaHA particle size range of 25-45 microns and should be injected with a 25 gauge Outer Diameter (O.D.) to 27 gauge Inner Diameter (I.D.) needle. The same size needle should be utilized throughout the trial for an individual subject and needle size will be collected in the electronic case report form.

8.1.2 Disposition of investigational product(s)

Radiesse has been FDA approved for injection into the face since 2006 (PMA P050037 and PMA P005052), and was approved for hand augmentation to correct volume loss in the dorsum of the hand in 2015 (PMA P050052/S049, see IFU **Appendix A**). This same Radiesse formulation will be used in the study for injection, as approved in the indication for hand augmentation to correct volume loss in the dorsum of the hand. Radiesse will be mixed with 2% lidocaine HCl prior to injection – an approved use of Radiesse.

8.2 Treatment administration

8.2.1 Randomization Procedures

The study is not a randomized trial, and there are no randomization procedures.

8.2.2 Treatment method

Prior to injection, Radiesse will be mixed with 0.26cc of 2% Lidocaine HCl. Volume injected as well as any observed AEs will be recorded. A maximum of 2 1.5cc Radiesse syringes will be injected per hand, per treatment visit. Treatment and retreatment visits will be scheduled per Table 2. There will be no touch-up treatments performed in the study. Subjects are to be given a 30-day take-home diary on which to record AEs that may occur before their next visit (copy provided in **Appendix B**).

Step-by-step injection instructions are as indicated below from the IFU in Appendix A.

Technique for Mixing Radiesse injectable implant and 2% Lidocaine HCI

The following components are required for the percutaneous injection procedure and mixing Radiesse injectable implant with lidocaine:

- Radiesse injectable implant syringe(s) 1.5cc
- Sterile 27 gauge, 0.5" regular-wall needle with luer lock connector
- 3.0cc sterile polypropylene luerlock syringe (
- 0.2cc of 2% lidocaine HCl for injection, USP solution (not supplied by Merz North America, Inc.)
- Sterile Female-to-female luer lock connector

The Radiesse, sterile needles, 3.0cc sterile polypropylene mixing syringe (), and the female-to-female luer lock connector () will be provided in a kit by Merz for the study. The lidocaine will not be supplied by Merz.

Component Assembly and Mixing Instructions

- 1. Remove foil pouch from the carton containing the Radiesse injectable implant syringe. Open the foil pouch by tearing at the notches (marked 1 and 2), and remove the syringe from the foil pouch. *There is a small amount of moisture normally present inside the foil pouch for sterilization purposes; this is not an indication of a defective product.*
- Assemble the components and perform the mixing using sterile technique (see Figure 3).

Figure 3. Radiesse mixing components. Left to right: Female-tofemale luer lock connector, Radiesse 1.5cc syringe, 3.0cc mixing

- 3. Draw the 0.2cc lidocaine into a 3.0cc sterile polypropylene mixing syringe fitted with a sterile 27 gauge, 0.5" needle.
- 4. Tap the mixing syringe, containing 0.26cc lidocaine and depress its push rod to remove all excess air.

- 5. Remove the sterile 27 gauge, 0.5" needle.
- 6. Remove the luer syringe cap from the distal end of the Radiesse syringe and firmly connect the mixing syringe to the Radiesse syringe using the female-to-female luer lock connector (see **Figures 4** and **5**).

Figure 5. Connecting Radiesse syringe to the mixing syringe.

7. Mix the lidocaine and Radiesse by alternately depressing the plungers, first on the mixing syringe and then on the Radiesse syringe for 10 mixing strokes (each mixing stroke is 1 complete compression of the mixing syringe plunger followed by 1 complete compression of the Radiesse syringe plunger). Plungers are compressed firmly and quickly, at about 2 compressions per second (Figure 6).

- 8. After mixing, remove the mixing syringe and the female-to-female luer lock connector and discard.
- 9. Fit the syringe containing the lidocaine and Radiesse mixture with a 27 ID gauge injection needle by twisting the syringe of Radiesse onto the luer lock fitting of the needle. *Tighten the needle securely to the syringe*. If excess Radiesse is on the surface of the luer lock fittings, it will need to be wiped clean with sterile gauze.
- 10. Proceed to the "Injection Procedure" below.

Injection Procedure for Hand Augmentation

- 1. Prepare subject for percutaneous injection using standard methods. Have the subject wash both hands with soapy water producing friction for 5-10 minutes and then prepare hands with suitable antiseptic. The treatment injection site may be marked for planned injection sites. Jewelry should be removed prior to injection and until post-procedure swelling has resolved.
- 2. Using the syringe of Radiesse injectable implant that has been mixed with lidocaine using the procedure described in "Mixing Instructions" above, and fitted with the injection needle, slowly push the syringe plunger until Radiesse injectable implant extrudes from the end of the needle performing aspiration before bolus injection to avoid intravascular injection. If leakage is noted at the luer fitting, wipe it clean with sterile gauze. It may be necessary to tighten the needle, remove the needle and clean the surfaces of the luer fitting or, in extreme cases, replace both the syringe and the needle. A new injection needle may be used for each syringe, or the same injection needle may be connected to each new syringe.
- 3. Locate the initial site for injection. Subjects are to receive injections in the dorsum of the hands between the 1st and 5th metacarpals. Injection should initially occur between the 2nd and 4th metacarpals, taking care not to inject close to the metacarpophalangeal joints. If necessary to achieve optimal correction, injection is also allowed between the 1st and 2nd, and 4th metacarpals.
- 4. Skin tenting should be performed to separate the skin from vascular and tendinous structures by using the thumb and forefinger of the non-injecting hand to lift skin over the dorsal aspect of the hand being treated.
- 5. Advance the needle between the subcutaneous layer and superficial fascia with the syringe parallel to the dorsum of the hand. Carefully push the plunger of the Radiesse injectable implant syringe to start the injection and inject the Radiesse injectable implant material in small boluses, 0.2 0.5cc/bolus. No more than 0.5cc should be injected per bolus. The number of boluses will vary depending on the extent of treatment desired. No more than 3cc of Radiesse injectable implant (2 syringes) will be injected per hand, per treatment session.
- 6. If significant resistance is encountered when pushing the plunger, the injection needle may be moved slightly to allow easier placement of the material or it may be necessary to change the injection needle.

- 7. Immediately after injection, cover the injection site with a sterile 4x4 gauze and have the subject sit on this hand while the contralateral hand is being injected. This warms the Radiesse injectable implant making it more malleable for later massaging.
- 8. Treat the contralateral hand in the same manner as described in steps 2 through 6 above.
- 9. Immediately after injection of the contralateral hand, cover the injection site with a sterile 4x4 gauze and have the subject sit on this hand.
- 10. While the contralateral hand is warming, remove the gauze from the hand that was initially injected, have the subject make a fist with this hand, and gently massage the dorsum of the hand until Radiesse has been evenly spread across the dorsum, remaining distal to the wrist crease and proximal to the metacarpophalangeal joints.
- 11. Use a 1:1 correction factor. No overcorrection is needed.

9 STUDY ASSESSMENTS

9.1 Clinical evaluations

9.1.1 Training and masking of MHGS evaluators

The MHGS (Figure 1) will be used to measure clinical effectiveness of the Radiesse hand treatments by a masked evaluator performing live dorsal hand assessments. There will be one masked MHGS evaluator per site. The MHGS is an ordinal scale and therefore ratings will be made based on a "snap-shot" at a time point and will not be based on a comparison to a pre-treatment photograph. The evaluator will remain masked throughout the study and blinded to knowledge of 0 to 3 repeat treatments during the study. Prior to study initiation, the masked evaluator will be trained and qualified by the study sponsor to perform MHGS assessments. Training will consist of an instructional webinar and qualification will consist of the masked evaluator trainee scoring 2 25subject photo booklets, at least 1 week apart for intra-rater weighted Kappa analyses prior to study initiation. Retraining will occur if a minimal weighted Kappa value is not achieved (> 0.60), with qualification required prior to screening subjects for the study and Radiesse treatment in the study. If a repeat hand treatment is scheduled during a study visit, the MHGS assessment will be completed prior to treatment. To ensure that the blind is maintained, subjects will have their upper body and face hidden behind a barrier screen with only their hand visible to the masked evaluator. Subjects will be asked to remain silent during the MHGS evaluation process. Masked evaluators will not be allowed to discuss treatment schedules with treatment investigators and study staff at the site, and will not enter data on case report forms (CRFs) that contain information that would break the blind.

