7.2 Inclusion criteria

Only subjects meeting all of the following inclusion criteria will be considered for study enrollment:

- 1. Has hands rating 2, 3, or 4 on the validated MHGS as determined by a live, masked evaluator.
 - Left and right hand with a rating of 4 of the validated MHGS will be assigned to Group A.
 - Left and right hands with a rating of 2 or 3 on the validated MHGS will be assigned to Group B.
- 2. Has left and right hands with a rating of 2 or 3 on the validated MHGS as determined by a live, masked evaluator if screened for Group B.
- 3. Is at least 22 years of age.²
- 4. Has signed an ICF.

² Pediatric populations or subpopulations generally do not suffer from the hand condition the device is intended to treat in the study protocol.

- 5. Understands and accepts the obligation not to receive any other procedures in the dorsum of the hands through the end of the study.
- 6. Understands and accepts the obligation and is logistically able to present for all scheduled follow-up visits and meet all study requirements.

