9.2 Visit schedule

Screening and Enrollment

Enrollment will be limited to 250 subjects for the study. The Sponsor will oversee enrollment and be in direct communication with the investigational sites to make all efforts not to exceed the enrollment target of 250 subjects, and to ensure that Groups A and B (described in Section 7) are fully enrolled. Presenting subjects may be pre-screened to the selection criteria identified in Sections 7.2 and 7.3 above. If it is determined that a presenting subject meets these selection criteria, the subject will be given an ICF to review and sign.

Upon the subject's provision of informed consent to participate in the study, the subject will be enrolled in the study and assigned a study ID number. The number will contain 3 parts – trial identification code (GF = GradeFour), site identification number, and subject enrollment order number. For example, the third subject enrolled will receive study ID number GF-1-03. The masked evaluator will assess hands on the MHGS to meet hand rating requirements for inclusion. Enrolled subjects will be assigned to Group A or B based on baseline MHGS ratings until both groups are fully enrolled. Females of childbearing age will complete a urine pregnancy test. Study information including demographics and concomitant medications will be recorded, and photographs will be taken of each hand. After photographs, subjects will complete all of the hand function tests. If the subject is one of the first 10 enrolled at a site, the hand function tests will be repeated, as administered by a different hand function testing investigator. At this time, subjects will receive a Radiesse treatment. A take-home 30day diary will be given to the subject. A physician will assess the subject's hands for AEs. Subjects will be scheduled for a phone visit to be conducted 72 hours after treatment.

Follow-Up Evaluations

72 hours after enrollment: All subjects will be scheduled for a phone visit 72 hours after initial treatment to assess for AEs. Subjects will be reminded to continue daily entries into their 30-day diary.

Week 2: 14 ± 3 days from enrollment, all subjects will return for a follow-up visit. Changes in concomitant medications will be recorded by the study staff. Subject self-assessment of aesthetic improvement will be performed using the GAIS.

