12.1 Determination of sample size

The primary endpoint will be based on a non-inferiority hypothesis test comparing the 6month rate of device/injection-related severe AEs in the MHGS4 (Group A) subjects versus the MHGS2-3 (Group B) subjects. Based on the pre-market study data, an expected rate of severe adverse events is 17% for both groups, and the test will be based on a 12% non-inferiority margin. This margin allows for adequate power of the planned hypothesis test with a reasonable sample size and will provide assurance that the severe AE rate in the MHGS4 subjects is not unacceptably higher given the expected benefit in these subjects. The test will be based on a one-sided Farrington-Manning likelihood score test of binomial proportions at a one-sided 0.05 alpha level. A maximum of 250 subjects with MHGS grades 2, 3 and 4 at baseline (at least 50% with both hands rated MHGS 4) will be enrolled in at least 5 sites and a maximum of 12 sites in the US. Allowing for some attrition, a total of 244 subjects (122 in each group) at 6 months will provide approximately 80% power to conduct the hypothesis test. Based on an expected attrition rate of 5% per year, a minimum of 225 evaluable subjects are required to provide 2-year follow-up data. Safety and effectiveness data that are collected after 6 months and up to 2 years will be presented descriptively.

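### The one evaluator per site who decides Group A or B is qualified only on agreement with their own scores, so a consistent grade 3/4 error would pass and can, under stated conditions, make non-inferiority easier to claim

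*Protocol*

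**What the plan says.** Protocol section 9.1.1 has the sponsor train evaluators by webinar and qualify them on two scorings of 25-subject photo booklets, at least a week apart, "for intra-rater weighted Kappa analyses prior to study initiation". Retraining follows unless weighted kappa exceeds 0.60. On staffing it says: "There will be one masked MHGS evaluator per site".

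That evaluator also decides group membership. Section 9.2: "The masked evaluator will assess hands on the MHGS to meet hand rating requirements for inclusion", and then "Enrolled subjects will be assigned to Group A or B based on baseline MHGS ratings until both groups are fully enrolled". Section 7.2 sets the rule for Group A: "Left and right hand with a rating of 4 of the validated MHGS will be assigned to Group A". Group B needs both hands at 2 or 3.

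Neither document provides an inter-evaluator comparison, a reference score, a second reader or a central photograph check for the MHGS. Baseline photographs are taken (section 9.2) but are not used to confirm the grade. Two independent raters are planned only for hand function (sections 6.1 and 9.1.3). SAP section 4.2 covers masking, not agreement.

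**The concern.** The study is not randomized, so the baseline grade is the exposure in the primary comparison. Intra-rater kappa shows that an evaluator repeats their own scores. It does not show that the scores are right, or that the 5 to 12 site evaluators place the 3/4 boundary in the same place. Weighting also gives partial credit for one-grade errors, which are exactly the errors that move a subject between groups.

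Two things are at stake. Grade 4 may mean different things at different sites, in a study whose purpose is evidence on grade 4 hands. And mixing the groups can shrink P_A - P_B. In a superiority trial that would be conservative; in a non-inferiority test it favours the claim.

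**Working it through.** **Inputs from the documents** (Protocol section 12.1, SAP section 3): "an expected rate of severe adverse events is 17% for both groups"; "the test will be based on a 12% non-inferiority margin"; Farrington-Manning score test, one-sided alpha 0.05; 122 per group at 6 months for about 80% power.

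**Assumptions, because the documents give no figures:** the true risk by grade, the share misgraded, the mix of grades screened, the mix of grades in the booklet, and the kappa weights.

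**1. The plan's own figure.** n per group = (1.645 + 0.842)² × 2 × 0.17 × 0.83 / 0.12² = 121.2, so 122. Exact binomial enumeration of the Farrington-Manning test at 122 per group gives 79.7% power at 17% vs 17%. At the margin (29% vs 17%) it rejects 5.0% of the time. The design reproduces.

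**2. Does the check catch a consistent error?** A rater who scores every grade 3 as 4, or every grade 4 as 3, in the same way both times has intra-rater kappa 1.00. In a simulation with 10% random one-grade noise on each reading (linear weights, five photos at each of grades 0 to 4), mean kappa was 0.93 for the over-grader and 0.87 for the under-grader. Essentially all such raters passed 0.60.

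**3. Size, with true rates 29% and 17% and one risk shared by grades 2 and 3.** If a share f of labelled Group A is really grade 2 or 3, P_A = 0.29 - 0.12f. If a share g of labelled Group B is really grade 4, P_B = 0.17 + 0.12g.

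| Misgraded share | Expected difference | False non-inferiority |
|---|---|---|
| none | 12.0 points | 5.0% |
| f = 10% | 10.8 | 7.8% |
| f = 20% | 9.6 | 11.8% |
| f = 30% | 8.4 | 17.0% |
| g = 20% | 9.6 | 11.5% |

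If f = 20% at only 1 of 12 equal sites, the overall share is 0.20/12 = 1.7%, the difference is 11.8 points and the chance is 5.4%. At 3 of 12 sites it is 6.3%.

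**4. Direction.** Take screened grades 4:3:2 in the ratio 2:1:1, and let q be the share of the affected grade that is misgraded.

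- Under-grading: P_B = (0.17 + 0.29q)/(1 + q). At q = 25%, P_B = 19.4%, the difference is 9.6 points and the chance is 11.5%. True grade 4 hands enter Group B and P_A is unchanged, so the difference always shrinks when grade 4 risk is higher.
- Over-grading: P_A = (0.29 + 0.5q·p3)/(1 + 0.5q) and P_B = [0.5·p2 + 0.5(1 - q)·p3]/[0.5 + 0.5(1 - q)].
  - With p2 = p3 = 17% and q = 50%: 26.6% vs 17.0%, 9.6 points, 11.8%.
  - With a gradient of 13%, 21%, 29% and q = 50%: 27.4% vs 15.7%, 11.7 points, 5.6%.
  - Same gradient and q = 100%: 26.3% vs 13.0%, 13.3 points, 2.8%. Group B is left with grade 2 only, and the difference widens.
- Equal risk in all grades: no change.

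**5. Which agreement statistic would see it?** Take a rater who calls every grade 3 a 4, compared with a correct score, with five photos at each of grades 0 to 4.

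- Linear weighted kappa: observed disagreement 5/25 = 0.20, chance disagreement 1.72, so 1 - 0.20/1.72 = 0.88. Passes.
- Raw agreement on 4 vs 2-3 among the 15 photos of grades 2 to 4: 10/15 = 67%. Passes a 0.60 bar.
- Unweighted kappa on 4 vs not-4: observed 0.80, chance 0.2 × 0.4 + 0.8 × 0.6 = 0.56, so 0.24/0.44 = 0.55. Fails.

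For a rater who calls every 4 a 3, weighted kappa is 0.87 (passes) and the 4 vs not-4 kappa is (0.80 - 0.80)/0.20 = 0.00 (fails).

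**The case against.** The strongest defence is that the scale is described as validated, section 7 gives written anchors for the grades, evaluators must qualify before screening, and both hands must grade 4 for Group A. The last point has real weight: an isolated error on one hand does not move a subject into the other group. It gives no protection against a shifted boundary, which affects both hands alike. The by-site subgroup analysis in SAP section 7.11 may show that sites differ, but it cannot say whether grading is the reason. So these measures make large study-wide misgrading less likely without testing for it.

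The objection also limits the direction and the size, and this stands. A reader might infer that any consistent 3/4 error biases the trial toward non-inferiority. The documents do not support that: they give no risk by grade, and step 4 shows that over-grading can be neutral or work against the claim. Under the plan's own expectation of 17% in both groups, with no variation by grade, misgrading has no effect. Still, a non-inferiority test has to hold when grade 4 is truly worse, and section 7 itself expects that grade 4 hands might receive higher injection volumes.

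A reader might also model equal misgrading in both directions: 20% each way gives 26.6% vs 19.4% and 22.6% false non-inferiority. That pattern needs opposite biases in balance across sites, or random noise, which intra-rater kappa does address. It does not describe one evaluator with a shifted boundary, so it is not used as the measure of size here.

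**Conclusion.** The gap is real: one evaluator per site determines the exposure variable, and the only qualification cannot detect a self-consistent error at the boundary that defines it. The consequence is conditional. It needs a true excess risk in grade 4 hands, and either under-grading or over-grading with similar risk in grades 2 and 3. With 29% vs 17% assumed, a 20% one-way error across the whole study roughly doubles the chance of a false non-inferiority conclusion, from 5.0% to 11.8% (Group A contaminated) or 11.5% (Group B contaminated). At 1 of 12 sites the effect is negligible, at 5.4%. With the minimum of 5 sites, one evaluator would grade about a fifth of the subjects. The documents do not show that misgrading on this scale is likely; they show that the plan could not tell. The remedy costs little, so the change should be made, but the point does not by itself invalidate the primary analysis.

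**What to change.** In section 9.1.1, state that all evaluators score the same booklets. Before screening starts, use those scores to compute for each evaluator an unweighted kappa on grade 4 versus not-4 against a sponsor reference score. Failing a reference, compare with the consensus of the other evaluators, accepting that this cannot reveal a bias all of them share. Apply the existing > 0.60 retraining rule to this kappa as well as to the intra-rater kappa. Do not rely on overall weighted kappa or on raw agreement at 0.60; step 5 shows that both let the error through.

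The bar catches gross shifts only, so the booklet should hold enough grade 3 and 4 photographs. With five per grade, a rater who calls four of the five grade 3 photos grade 4 has observed agreement 0.84 and chance agreement 0.2 × 0.36 + 0.8 × 0.64 = 0.584, so kappa is 0.256/0.416 = 0.62 and still passes. Reporting the count and direction of 3/4 disagreements beside the kappa would show this.

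Cost: one sentence in the protocol, one reference scoring of the booklet and a small calculation. No extra subjects, visits or site readings are needed if the booklets are common to all sites. The downside is that some evaluators may need retraining before they can screen. If screening is already past, blinded central re-grading of the baseline photographs with a sensitivity analysis would address the same gap, at the cost of new readings.
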